## **17.2. Ethical Conduct of the Study**

The Sponsor will use information developed in this clinical study in connection with the development of A-101 Solution and, therefore, may disclose it as required to other clinical Investigators participating in other studies and to regulatory agencies. In order to allow the use of the information derived from this clinical study, the Investigator understands that he/she has an obligation to provide all data produced during this study to the Sponsor.

The Sponsor considers that clinical data (complete or incomplete) constitute financially sensitive information. Consequently, the Sponsor requires that discussion of results in any form, electronic, verbal, or written before study completion and full reporting should only be undertaken with the Sponsor's prior written consent.

Individual patients' medical information obtained as a result of this study is considered confidential. The Investigator and the study center will adhere to all applicable laws relating to the protection of patient information. To assure that patients' confidentiality is maintained, patients' data will be identified by a study-assigned number.

All Sponsor personnel will handle patients' data in a confidential manner in accordance with applicable regulations governing clinical research. Subjects' records will be inspected only in connection with this research project. Information generated as a result of a subject's participation in this study may be disclosed to third parties for research and regulatory purposes in any country as determined by the Sponsor. However, subjects will not be individually identified but will be referred to only by the study assigned number.

## **17.3. Regulatory Documents**

The investigator must maintain a study file containing current and complete regulatory documentation in compliance with the current ICH E6 GCP guideline. This file will be reviewed as part of the routine monitoring for this study.

## **17.4. Contractual Requirements**

A contractual agreement will be signed between Aclaris Therapeutics, Inc. and each investigator. This document will contain supplemental information, including financial terms, confidentiality, study schedule, third party responsibility, and publication rights.

## APPENDIX 1. A-101-WART-302 SUBJECT INSTRUCTION SHEET

Please follow these instructions carefully. Contact the study staff at the telephone number noted below if you have any questions about the study:

Contact: \_\_\_\_\_ Telephone: \_\_\_\_\_

### **THROUGHOUT THE STUDY:**

- Continue your routine cleansing regimen except avoid vigorous scrubbing of the identified common warts (e.g., abrasive cleansing pads, abrasive cleansers, etc.).
- Continue your routine skin care products.
- Avoid exposing the identified common warts to excessive natural or artificial ultraviolet radiation (e.g., sunlight, tanning beds) and use sunscreen on the wart, if excessive exposure cannot be avoided.
- Avoid activities that might irritate the identified common warts.
- Bring this subject instruction sheet and subject diary with you to each visit.

### **STARTING WITH VISIT 2:**

- On visit days, do not apply any topical products (e.g., moisturizers, sunscreens) to the identified common wart, except for routine cleansing products, within **12 hours** prior to the visit
- After any study visit where a study medication treatment occurred do not:
  - Wash/submerge the treated common warts for at least **6 hours** after the treatment
  - Apply any topical products to the treated common warts for at least **6 hours**
  - Occlude, bandage or otherwise cover the common wart treatment area (loose-fitting clothing is permissible) for at least **6 hours**.
  - Parents/legal guardians of children must ensure that the child does not put the treated area in their mouth, or eyes, until completely dry after the application. If the treated area is not completely dry 10 minutes after the application, the area should be blotted dry.

**STUDY MEDICATION:** The study medication provided to you is only to be used as instructed.

Please ask your doctor or staff if you have any questions about its use.

### **STUDY VISIT SCHEDULE:**

|          |          |
|----------|----------|
| VISIT 2: | VISIT 3: |
|----------|----------|

Aclaris Therapeutics, Inc.

Protocol Number: A-101-WART-302

Amendment 3: Version 5 14 February 2019

|             |             |             |             |
|-------------|-------------|-------------|-------------|
| Date: _____ | Time: _____ | Date: _____ | Time: _____ |
| VISIT 4:    |             | VISIT 5:    |             |
| Date: _____ | Time: _____ | Date: _____ | Time: _____ |
| VISIT 6:    |             | VISIT 7:    |             |
| Date: _____ | Time: _____ | Date: _____ | Time: _____ |
| VISIT 8:    |             | VISIT 9:    |             |
| Date: _____ | Time: _____ | Date: _____ | Time: _____ |
| VISIT 10:   |             | VISIT 11:   |             |
| Date: _____ | Time: _____ | Date: _____ | Time: _____ |
| VISIT 12:   |             | VISIT 13:   |             |
| Date: _____ | Time: _____ | Date: _____ | Time: _____ |

### At Home Study Administration Days:

[figure not shown]
- Do not apply any topical products (e.g., moisturizers, sunscreens) to the identified common wart, except for routine cleansing products, within **12 hours** prior to the administration
- After the application of the study medication do not:
  - Wash/submerge the treated common wart for at least **6 hours** after the treatment
  - Apply any topical products to the treated common wart for at least **6 hours**
  - Occlude, bandage or otherwise cover the common wart treatment area (loose-fitting clothing is permissible) for at least **6 hours**.

Parents/legal guardians of children must ensure that the child does not put the treated area in their mouth, or eyes, until completely dry after the application. If the treated area is not completely dry 10 minutes after the application, the area should be blotted dry.

### At Home Study Medication Application:

- Wash your hands prior to completing study medication treatment.
- Visually inspect the applicator for damage. If the applicator appears damaged do not use it for the treatment.
- Do not apply the study medications to eyes, nose, mouth, mucous membranes, or open wounds.
- Wear nitrile examination gloves during the treatment that were provided to you by your doctor. Latex gloves are prohibited.
- Thoroughly cleanse the identified common wart by firmly rubbing with a swab/wipe wetted with 70% isopropyl alcohol that was provided to you by your doctor.
- Using firm pressure and with the tip of the applicator held over the wart, squeeze in the middle of the applicator to apply one drop of study medication onto the identified common wart. Using the smaller side of the applicator tip, firmly move the applicator around in a circular motion to fully saturate the lesion. Apply the study medication for approximately 15 seconds.
- Minimize exposure to the surrounding normal skin.
- During the treatment process remove excess study medication from the surrounding skin using a clean absorbent wipe.
- Ensure the each identified wart is fully saturated with study medication at the end of the approximately 15 second application.
- Allow the treated wart to remain undisturbed for approximately 15 seconds.
- After approximately 15 seconds repeat the approximately 15 second application process.
- Repeat the application/waiting cycle until the study medication has been applied to the identified common wart up to 3 times.
- Absorb any remaining A-101 study medication and dry the treated common wart and the surrounding skin without wiping or rubbing.
- Document, in your treatment diary, the number of times the identified common wart is treated during a treatment.
- After applying the study medication, the cap should be put back on the applicator, the used applicator should be put in one of the used nitrile gloves (after removal), knotted at the end and placed in a biohazard bag. The biohazard bag, with the used applicator in the glove, should be placed in the plastic bag you brought the applicator home in, and returned to the site for accountability.

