## 7. STUDY DESIGN

This is a phase 3, multicenter, randomized, vehicle controlled, double blind parallel group study designed to evaluate the efficacy and safety of A-101 45% compared to Vehicle in subjects with common warts.

During the study, the investigator will identify at least 1 and up to 6 common warts to be treated twice a week for up to 8 weeks (maximum of 16 treatment applications)

Subjects will be required to complete a total of 13 study visits. The protocol defined study visits are:

- Visit 1 (Day -13 to 0) screening
- Visit 2 (Day 1)\* randomization; study medication treatment
- Visit 3 (Day 8)\* study medication treatment
- Visit 4 (Day 15)\* study medication treatment
- Visit 5 (Day 22)\* study medication treatment
- Visit 6 (Day 29)\* study medication treatment
- Visit 7 (Day 36)\* study medication treatment
- Visit 8 (Day 43)\* study medication treatment
- Visit 9 (Day 50)\* study medication treatment
- Visit 10 (Day 60) follow up evaluations, no identified Wart retreatment
- Visit 11 (Day 78) follow up evaluations, no identified Wart retreatment
- Visit 12 (Day 106) follow up evaluations, no identified Wart retreatment
- Visit 13 (Day 137) follow up evaluations, no identified Wart retreatment; end of study

\*The second weekly application will be applied by the subject/parent/legal guardian at home (Day 4, 11, 18, 25, 32, 39, 46, and 53).

Refer to [Table 2](#) for a complete list of protocol required study assessments.

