### **10.5. Study Medication Treatment**

The study medications are for external, topical use only and are to be applied only to those subjects that have been properly consented and randomized to the study.

The investigational center staff member must comply with the study medication storage conditions outlined in Section [10.1](#)

During Visit 2-Visit 9 (if the identified common wart meets the criteria for retreatment), the investigational study staff will select the appropriate study medication applicator for treatment of a specific subject. Subjects ages 18 years of age and older will apply the appropriately labeled A-101 study medication to the identified common wart in the presence of the treating investigator or investigational staff that has been trained on the protocol. The second weekly application of the A-101 study medication will be applied by the subject at home (Days 4, 11, 18, 25, 32, 39, 46, and 53). The second weekly treatment will be determined by the PWA assessment performed during the in-office visit. If the identified common wart meets the criteria for retreatment, then the subject will apply the A-101 study medication at home.

Subjects between the ages of 1 and 17 years of age will have their A-101 study medication applied in the office by a parent or legal guardian in the presence of the treating physician or a member of the investigational site staff during Visit 2-Visit 9. The second weekly A-101 study medication application will be applied at home by a parent or a legal guardian (Days 4, 11, 18, 25, 32, 39, 46, and 53). The second weekly treatment will be determined by the PWA assessment performed during the in-office visit. If the wart meets the criteria for retreatment, then the subject will apply the A-101 study medication at home.

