**Retreatment Criteria:**

At Visit 3-9, if the identified common wart has a **PWA grade of >0** then the subject will receive re-treatment with the A-101 study medication treatment. However, treatment with the A-101 study medication should not be applied if any of the following criteria apply to the identified common wart:

- The common wart has a pre-treatment LSR grade of 3 (severe) for any sign or symptom AND the grade has increased compared to the previous visit.
- The common wart is, in the investigator's opinion, not appropriate for a retreatment (the investigator must note the reason on the subject's Comments CRF page).
- The common wart, in the Investigator's opinion, cannot be visualized so the Investigator cannot assess the PWA.

If the identified common wart meets the criteria for re-treatment during the in-office visit (PWA>0), then the subject/parent/legal guardian should treat the common wart at home on the protocol defined at home treatment days (Days 4, 11, 18, 25, 32, 39, 46, 53. A window of +1 day is allowed). If the subject is unable to tolerate treatment the day of an at home treatment visit due to severe skin irritation, then the treatment should be held and the investigational site should be notified.

Subjects whose identified common wart(s) is assessed at a particular visit (V3-V9) to be a PWA=0 will not have the that common wart re-treated at that visit (or retreated at the second at home application that week).

[figure not shown]

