## **10.7. Applying Study Medication**

All subjects that are between the ages of 1 and 17 will have their A-101 study medication applied by a parent/legal guardian. Parents/legal guardians of children must ensure that the child does not put the treated area in their mouth, or eyes, until completely dry after the application. If the treated area is not completely dry 10 minutes after the application, the area should be blotted dry. For in-office visits, the subject's parent or legal guardian will apply the A-101 study medication in front of a member of the investigational study staff to ensure there is a clear understanding regarding how the study medication should be handled.

Subjects 18 years of age and older will apply their A-101 study medication to his/her identified common warts in the presence of the treating physician or member of the investigational staff during in-office visits. The second weekly application will be performed at home.

The following instructions will be used by all subjects/parents/legal guardians applying A-101 study medication to all identified common warts:

- Do not apply the study medications to eyes, nose, mouth, mucous membranes, or open wounds
- Wear nitrile or vinyl examination gloves during the treatment; **latex gloves are prohibited (All subjects will be supplied with nitrile or vinyl examination gloves to be used for at home applications)**
- Thoroughly cleanse the common wart by firmly rubbing with a swab/wipe wetted with 70% isopropyl alcohol
- Using firm pressure and with the tip of the applicator held over the wart, squeeze in the middle of the applicator to apply one drop of study medication onto the common wart. Using the smaller side of the applicator tip, move the applicator around in a circular motion to fully saturate the lesion. Apply the study medication for approximately 15 seconds.
- Minimize exposure to the surrounding normal skin
- During the treatment process remove excess study medication from the surrounding skin using a clean absorbent wipe.
- Ensure the identified common wart is fully saturated with study medication at the end of the ~15 second application
- Allow the treated wart to remain undisturbed for ~15 seconds
- After ~15 seconds repeat the ~15 second application process
- Repeat the application/waiting cycle until the study medication has been applied to each identified Wart up to 3 times.

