- If severe erythema and edema develop, then the treatment cycle should be discontinued for that specific treatment application.
- Absorb any remaining A-101 study medication and dry the common wart and the surrounding skin without wiping or rubbing.

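### The readable home instruction sheet omits the stop, hold-and-notify and parent-applies rules stated in the protocol body, and Section 10.5 contradicts itself on who applies the drug at home for ages 1–17

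*Protocol*

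**What the plan says.** **Protocol body.** Section 10.7 introduces its application steps with "The following instructions will be used by all subjects/parents/legal guardians applying A-101 study medication to all identified common warts". One of the steps is "If severe erythema and edema develop, then the treatment cycle should be discontinued for that specific treatment application". The Synopsis (Study Drug Administration) carries the same stop rule. For home days, the Retreatment Criteria in Section 10.5 add that if the subject cannot tolerate treatment "due to severe skin irritation, then the treatment should be held and the investigational site should be notified". The Synopsis, Table 2 (footnotes 14 and 15), Section 10.5 and Section 10.7 all say that a parent or guardian applies the drug for ages 1–17. The Section 10.5 paragraph on that age group, however, ends: "If the wart meets the criteria for retreatment, then the subject will apply the A-101 study medication at home".

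**Instruction sheet.** Section 12.4 has Appendix 1 handed to every subject at Visit 1. Its home application list contains "Repeat the application/waiting cycle until the study medication has been applied to the identified common wart up to 3 times", and the next bullet is about absorbing leftover solution and drying. The sheet addresses its reader as the person applying the drug. It mentions parents only for keeping the treated area away from mouth and eyes and blotting it dry. It gives a telephone number for questions about the study.

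**Schedule.** Section 7 has warts "treated twice a week for up to 8 weeks (maximum of 16 treatment applications", and states: "The second weekly application will be applied by the subject/parent/legal guardian at home (Day 4, 11, 18, 25, 32, 39, 46, and 53".

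**The concern.** A stop rule and a home hold rule work only if the person holding the applicator knows them. After in-office treatment, Section 14.2.1 has staff observe the subject for at least 20 minutes. At home no site staff are present, so the written sheet is what the user can consult. Two of the three missing rules deal with severe local reactions, and the third deals with who handles a 45% hydrogen peroxide solution when the subject is a child. The stakes are subject safety and prompt notification of the site. No efficacy endpoint or analysis is shown to depend on this.

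**Working it through.** **Step 1: the two application lists side by side.**

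| Step | Section 10.7 | Appendix 1, home application |
|---|---|---|
| Wait about 15 seconds, then reapply | present | present |
| Repeat the cycle, up to 3 times | present | present |
| Discontinue the cycle if severe erythema and edema develop | present | **absent** |
| Absorb the remainder and dry without rubbing | present | present, directly after the repeat step |

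The steps on either side of the stop bullet match almost line for line. The list is readable as a continuous sequence, so the absence of this bullet does not come from a missing figure.

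**Step 2: the hold-and-notify rule.** Section 10.5 states it specifically for home treatment days. The readable text of Appendix 1 contains neither a hold instruction nor a trigger for calling the site. The telephone number is for questions.

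**Step 3: who applies the drug for ages 1–17.** The body assigns this to a parent or guardian in four places. The readable text of Appendix 1 does not state it. Within the Section 10.5 paragraph on ages 1–17, an earlier sentence has the parent or guardian give the home application and the closing sentence has the subject give it. The two cannot both stand as written.

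**Step 4: how much of the treatment this covers.**

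- In-office applications (Section 7, Visits 2–9): Days 1, 8, 15, 22, 29, 36, 43, 50 = 8.
- Home applications (Section 7): Days 4, 11, 18, 25, 32, 39, 46, 53 = 8.
- Total: 8 + 8 = 16, which reproduces the stated maximum.
- Home share: 8/16 = 50%. At up to 3 cycles each, that is 8 × 3 = 24 of 16 × 3 = 48 cycles per wart.
- A-101 arm: 500/2 = 250 subjects. Home applications: 250 × 8 = 2,000.
- Ages 1–17: 100/500 × 250 = about 50 A-101 subjects. Home applications: 50 × 8 = about 400.

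The last two lines are scheduled ceilings. They count treatment occasions per subject, not affected subjects. They assume that every home application is given, although Section 10.5 makes each one depend on that week's in-office PWA, and they ignore dropout. The figure of 50 also assumes an even split within the age group. Randomization is stratified by site, not by age (Section 10.2).

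**Step 5: how long a held home dose could stay unknown.** If nobody calls the site, the next contact is the next visit. For seven of the eight home days this is nominally 4 days later (for example Day 4 to Day 8). For the last it is 7 days (Day 53 to Day 60), or 11 days if Visit 10 falls at the end of its +4-day window.

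**The case against.** The strongest reply is that the governing text contains all three rules and that the sheet is not the only way users learn them. Section 10.7 is expressly for everyone who applies the drug. The person who doses at home also applies it in front of staff at Visits 2–9. Section 10.6 requires staff to review the instructions at each in-office treatment visit. It also mentions application instruction sheets supplied after each of those visits, and the documents do not settle whether these are Appendix 1 or something else. A figure under the home administration days heading of Appendix 1 is not shown, so the second and third omissions can be asserted only of the readable text. Phase 2 local reactions are described as predominantly mild and transient (Section 5.2), and no rate of severe reactions is given. All of this stands as mitigation. It does not put the rules on the sheet. The review in Section 10.6 is worded around the steps that follow it, so it does not clearly reach the hold rule, which sits earlier in Section 10.5.

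Four stronger readings are tempting, and the documents do not support them.

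- A reader might infer that users would carry on through all three cycles during a severe reaction. Three is a ceiling, the diary records the number of applications, and SAP Section 3.3.1 tabulates treatments done in 1, 2 or 3 applications.
- A reader might infer that home holds go unreported. The diary comes to each visit, used applicators are returned, adverse events are elicited at each visit, and local skin reactions are graded at Visits 2–13. A held dose should surface at the next visit. What may be lost is promptness.
- A reader might infer that Amendment 2 first admitted children. The change log in Section 1.1 says only that the age range was broadened, and its entry for the preceding version already refers to guardians.
- A reader might call these applications unsupervised. For ages 1–17 the body has a parent or guardian apply the drug. The accurate description is that site staff are not present.

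**Conclusion.** The point holds as an internal inconsistency affecting safety instructions. The missing stop bullet is certain from the text. The other two omissions are certain only for the readable part of Appendix 1. The contradiction in the Section 10.5 paragraph on ages 1–17 is plain, and is probably a drafting slip that echoes the adult paragraph. The exposure is up to half of each subject's scheduled applications. The totals from Step 4 are upper limits on opportunity and do not estimate harm. The conclusion assumes that Appendix 1, or a sheet with the same content, is what users consult at home. If the sheets mentioned in Section 10.6 are separate and carry the three rules, the practical gap narrows, but Appendix 1 would still differ from the body.

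**What to change.** Reconcile Appendix 1 with Sections 10.5 and 10.7 so that sheet and body give the same instruction on three matters: discontinuing a cycle, holding a home treatment and notifying the site, and who applies the drug for ages 1–17. Check any separate sheet supplied under Section 10.6 against the same text. Reconcile the two conflicting sentences in the ages 1–17 paragraph of Section 10.5. Everything needed is already in the protocol, so no new clinical rule is proposed. The cost is a revised sheet with IRB approval and one corrected sentence in Section 10.5. The sample size and the analyses do not change.
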